8.3.5 Pregnancy

Not applicable since ongoing pregnancy is the primary endpoint of the study.

8.4 Study intervention Overdose

For this study, any dose of Crinone® greater than 90 mg/p.v./q.d in the single treatment group, or Crinone® at 90 mg/p.v./q.d and Duphasston® at 10 mg/p.o./b.i.d in the combination treatment group will be considered an overdose. The schedule can be seen in [Section 1.3](#). In case of an overdose, the participant will be assessed by Investigators as to whether they will continue participating in the study or not. Rescue medicines that are administered are not considered overdosing.

Even if it is not associated with an AE or a SAE, any overdose is recorded in the CRF and reported to drug safety in an expedited manner. Overdoses are reported on a SAE Report Form, following the procedure in [Appendix 3](#), section on Reporting Serious Adverse Events.

8.5 Pharmacokinetics

Not applicable.

8.6 Pharmacodynamics

Not applicable.

8.7 Pharmacogenetics

Not applicable.

8.8 Biomarkers

Not applicable.

8.9 Immunogenicity Assessments

Not applicable

9 Statistical Considerations

9.1 Statistical Hypotheses

For this open label, exploratory, randomized, control, pilot trial, there will be no confirmative hypothesis testing considered.

CCI

9.3 Populations for Analyses

The analysis populations are specified below. The final decision to exclude participants from any analysis population will be made during a data review meeting prior to database lock.

Analysis Set	Description
Intention-to-Treat (ITT)	The ITT Population will include all participants who receive at least one dose of randomized study intervention. Participants will be analyzed according to the study intervention they were initially assigned.
Per-Protocol (PP)	Includes all participants in ITT population without any major protocol violations.
Safety Population	Include all participants who have received at least one dose of study intervention. Participants will be analyzed according to the actual study intervention they received

9.4 Statistical Analyses

9.4.1 Endpoints

9.4.1.1 Primary Endpoints

- Ongoing pregnancy (at 10-12 weeks of pregnancy (8-10 weeks after ET))

Definition: The presence of viable intra uterine fetus detected by ultrasound examination in 12 weeks of pregnancy.

9.4.1.2 Secondary Endpoints

- β -hCG positive

Definition: A pregnancy diagnosed by the detection of β -hCG in serum

- Implantation:

Definition: The number of gestational sacs observed by ultrasound scan

- Clinical pregnancy

Definition: A pregnancy diagnosed by ultrasound of one or more gestational sacs or definitive clinical signs of pregnancy. It includes ectopic pregnancy. Note: Multiple gestational sacs are counted as one clinical pregnancy.

- Early abortion

Definition: The spontaneous loss of an intra-uterine pregnancy prior to 12 completed weeks of gestational age.

- Bleeding (luteal phase, vaginal)

Definition: The bleeding data will be collected in a CRF after each visit by Investigators according to original medical documents.

- Luteal phase bleeding: defined as the onset of any bleeding after ET and prior to the pregnancy test. The luteal phase bleeding rate will be assessed in each group and analysed according to the pregnancy outcomes.
- Vaginal bleeding is defined as any bleeding recorded in the CRF after a pregnancy test via serum β -hCG and is considered as an AE. The vaginal bleeding rate will be assessed and compared in both groups at each visit.

9.4.1.3 Safety Endpoint(s)

Safety parameters will include the incidence and severity of all AEs.

9.4.2 General Considerations

Descriptive Statistics

For the continuous parameters, the following statistics will be presented: Number (N) of participants, mean, standard deviation (SD), median, first quartile (q1), third quartile (q3), minimum, and maximum. The number of participants with missing values ('Missing') will be presented based on observed case data if necessary. An overall column will also be added where appropriate.

For categorical parameters, the total number ('N') of participants and percentages will be presented. The number of participants with missing values ('Missing') will be presented based on observed case data if necessary. An overall column will also be added where appropriate.

Method for handling missing data

Normally, missing data will not be imputed. If the participant does not have the required evidence for ovulation, follicular development, or pregnancy, then the participant will be counted as a failure for that particular endpoint.

Should a specific endpoint need another method to handle missing data, this will be specified in the Statistical Analysis Plan.

9.4.3 Analysis of Endpoints

Endpoint	Statistical Analysis Methods
Primary	
The analysis of the primary endpoint in this pilot study is essential for further planning of formal clinical trials. The analysis for the primary endpoint will estimate the ongoing pregnancy rate and its corresponding 95% CI for each group, and difference in ongoing pregnancy rate between combination medication and Crinone® and its corresponding 90% CI. The CIs for each treatment group will be calculated with the Clopper-Pearson method. The CI for the difference between the two treatment groups will be calculated with the Pearson chi-square test
 
Ongoing pregnancy rate: the number of ongoing pregnancies expressed per 100 ET cycles (from the start date of first ET to the End of Study).
 
Since the number of embryos transferred is medically known to have an impact on the chance of achieving an ongoing pregnancy rate, the rate of participants with only 1 embryo transferred within each arm will be examined. If the data suggest a possible imbalance between the two arms, pertinent subgroup analyses of the primary endpoint in participants with only 1 embryo transferred and in participants with 2 embryos transferred may be performed. Details will be specified in the Statistical Analysis Plan.

Secondary	
The analyses of secondary endpoints will take the similar manner as primary endpoint.
 
Implantation rate: The number of gestational sacs observed divided by the number of embryos transferred (usually expressed as a percentage, %).
 
β-hCG positive rate: the number of β-hCG positive participants expressed per 100 ET cycles.
 
Clinical pregnancy rate: the number of clinical pregnancies expressed per 100 ET cycles.

Endpoint	Statistical Analysis Methods
	
Luteal phase bleeding rate : the number of the participants with luteal phase bleeding expressed per 100 embryos transferred cycles.
 
Vaginal bleeding rate: the number of the participants with vaginal bleeding expressed per 100 embryos transferred cycles.

9.4.4 Safety Analyses

Safety Analyses will be performed using the Safety population.

Data on AEs will be collected on scheduled and unscheduled visits, based on information spontaneously provided by the participant and/or by questioning the participant. The most current version of Medical Dictionary for Regulatory Activities (MedDRA) and the World Health Organization Drug Dictionary (WHODRUG) coding dictionaries will be used for AEs, medical conditions, and concomitant medications. Number and percentage of patients with AEs or SAEs will be presented according to System Organ Class and the preferred term from the MedDRA dictionary.

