4.1 Overall Design

This is a Phase IV, local, single center, open label, pilot, randomized controlled clinical study to compare the efficacy and safety of Crinone® versus combination medication. The study population are infertile women who receive FET in ACs. This study plans on including 334 participants from a single reproductive center over 25 months. Participants that enter the study will be randomized into either of the two groups. The study intervention drug received by the participant is determined based on the result of randomization. The randomization procedure is described in [Section 6.3](#). The overall scheme of the study is in [Section 1.2](#) and the Schedule of Activities at each visit can be found in [Section 1.3](#).

The participants will sign an ICF; the participants are free to withdraw at any time without prejudice to their medical care, and they are not obliged to state their reasons for withdrawal. Upon site initiation, the Investigator site will enroll the eligible participants who meet the inclusion and none of the exclusion criteria in a consecutive manner until the enrollment target is reached. The study will consist of a screening period, followed closely by procedures from endometrial transformation to ongoing pregnancy assessment, which lasts for approximately 75 days. Study treatment will start from the day of endometrial transformation (Day -5) until ongoing pregnancy assessment, which occurs between 10-12 weeks of pregnancy (8-10 weeks after ET). The middle number of 9 weeks (Day 63) after ET is used to define the study day with a window of 10 days on each side as leeway. The treatment will be administered for approximately 75 days.

Relevant data according to study requirements will be recorded in standard CRF. When the study starts, this reproductive center will include participants who enter the cycle. The information of the qualified yet excluded participants who have signed ICFs will be recorded, and the reason for their exclusion will also be recorded in the CRF. If a participant has entered the study and later discontinue their study intervention, the reason for discontinuing the study intervention will be recorded in the CRF.

[figure not shown]
Participant follow-up will occur until her ongoing pregnancy is confirmed and/or until End of Study (defined in [Section 4.4](#)).

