6.3 Measures to Minimize Bias: Study Intervention Assignment and Blinding

6.3.1 Study Intervention Assignment

Participants will be randomized in a 1:1 ratio to receive either Crinone® or the combination medication group on the day of ET.

The trial is designed as a single center trial, and randomization will be conducted on the ET day by using the block permutation method and stratified by age group (ages 20 to 35 years, or ages 35 years and over), which will guarantee that a balanced number of participants will be obtained between Crinone® and the combination medication groups inside each age stratum. If an error occurs (for example if the wrong list is used), the participant should continue with their assigned study intervention, and the next participant should still be assigned the next available number and study intervention of the correct list. The site must not attempt to “correct” for the error (i.e., if a participant is on the Crinone® list instead of the

combination medication group list, the site must not try to assign the Crinone® participant to the combination medication group list to offset this). Since ACCESS is an open-labeled observational study, baseline characteristic analysis will be presented to show whether the participants were well-stratified by age between the two study intervention groups.

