- Results in persistent or significant disability or incapacity
- Is a congenital anomaly or birth defect
- Is otherwise considered to be medically important. Important medical events that may not result in death, be life-threatening, or require hospitalization may be considered as SAEs when, based upon appropriate medical judgment, they may jeopardize the participant or may require medical or surgical intervention to prevent one of the outcomes listed above. Examples of such events include allergic bronchospasm requiring intensive study intervention in an emergency room or at home, blood dyscrasias or convulsions that do not result in inpatient hospitalization, or the development of drug dependency or drug abuse.

In this clinical study, any spontaneous abortion, ectopic pregnancy, should be considered as an SAE.

For the purposes of reporting, any suspected transmission of an infectious agent via a study intervention is also considered an SAE.

Events that Do Not Meet the Definition of an SAE

Elective hospitalizations to administer, or to simplify study intervention or procedures (e.g., an overnight stay to facilitate intravenous therapy) are not considered SAEs. However, all events leading to unplanned hospitalizations or unplanned prolongation of an elective hospitalization (i.e., undesirable effects of any administered study intervention) must be documented and reported as SAEs.

Events Not to Be Considered as AEs/SAEs

Medical conditions present at the initial study visit that do not worsen in severity or frequency during the study are defined as Baseline Medical Conditions, and are not to be considered AEs.

Recording and Follow-Up of AE and/or SAE

It is important that each AE report include a description of the event, its duration (onset and resolution dates and also onset and resolution times, when it is important to assess the time of AE onset relative to the recorded study intervention administration time), its severity, its causal relationship with the study intervention, any other potential causal factors, any study intervention given or other action taken, including dose modification or discontinuation of the study intervention, and its outcome. In addition, serious cases should be identified and the appropriate seriousness criteria documented.

Specific guidance is in the CRF Completion and Monitoring Conventions provided by the Sponsor.

Reporting Serious Adverse Events

Serious Adverse Events

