After about 13 to 15 days of ET, early detection of pregnancy will be done by measuring β - β -hCG levels using blood tests and the results will be recorded.

The following data will be collected:

- Date of pregnancy assessment
- β -hCG test results (positive or negative)
- Details of luteal phase bleeding, if any
- Recording of AEs
- Concomitant medications prescribed and reasons.

If the result of the pregnancy assessment is negative, procedures related to End of Study visit will be performed.

Visit 5 (Clinical Pregnancy Assessment)

If the result of the β -hCG pregnancy assessment is positive, it will be further confirmed by a clinical pregnancy assessment (by means of an ultrasound examination) 4 to 6 weeks after ET.

The following data will be collected:

- Date of pregnancy assessment
- Pregnancy status
- Positive pregnancy status has to be confirmed by ultrasound examination (presence or non-presence of gestational sac(s), gestational sacs with or without heartbeat, gestational stage at which ultrasound is performed is to be recorded and ectopic pregnancy).
- Details of vaginal bleeding, if any
- Recording of all AEs, expedited reporting of all SAEs

- Concomitant medications prescribed and reasons.

If the result of the pregnancy assessment is negative, procedures related to End of Study visit will be performed.

Visit 6 (Ongoing Pregnancy assessment)

Ongoing pregnancy is defined as the presence of viable intra uterine fetus detected by ultrasound examination in 12 weeks of pregnancy. The following data will be collected:

- End of study intervention date
- Singleton pregnancy / multiple pregnancy
- Status of ongoing pregnancy
- Early miscarriage, if any
- Details of vaginal bleeding, if any
- Recording of AEs
- Concomitant medications prescribed and reasons.

If the status of ongoing pregnancy is confirmed negative, all procedures related to End of Study Visit will be performed.

If the status of ongoing pregnancy is negative and if it is due to an abortion - the reason for abortion should be recorded.

End of Study

The date and the reason of the completion/withdraw from study intervention or study (see [Section 7.2](#)) will be collected.

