### 8.2 Definition of Analysis Populations and Subgroups

The analysis populations are specified below. The final decision to exclude subjects from any analysis population will be made during a data review meeting prior to database lock.

Analysis Population	Description
Intention-to-Treat (ITT) Population	The ITT Population will include all subjects who receive at least one dose of randomized study intervention after randomization. Subjects will be analyzed according to the study intervention they were initially assigned.
Per-Protocol (PP) Population	Includes all subjects in ITT population without any important protocol violations.
Safety Population	Include all subjects who have received at least one dose of study intervention after randomization. Subjects will be analyzed according to the actual study intervention they received.

The general use of the analysis populations in the different analyses are summarized as below.

Analyses	Analysis Population		
	Intent-to-Treat	Per Protocol	Safety
Baseline Assessments	✓		
Concomitant Therapies	✓		
Compliance and Exposure			✓

Analyses	Analysis Population		
	Intent-to-Treat	Per Protocol	Safety
Efficacy: Primary	✓	✓	
Efficacy: Secondary	✓	✓	
Safety			✓

If the Per Protocol analysis population includes at least 90% of subjects in the ITT analysis population, additional efficacy analyses on the Per Protocol analysis population will be omitted as the differences in the results based upon these two analysis populations are expected to be negligible.

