## 15.1.1 All Adverse Events

Unless otherwise stated, adverse events will be displayed in terms of frequency tables: by primary system organ class (SOC) in alphabetical order and preferred term (PT) in incidence descending order.

If an adverse event is reported for a given subject more than once during study intervention, the worst severity and the worst relationship to study intervention will be tabulated.

In addition, the following overall frequency table will be prepared by primary SOC in alphabetical order and PT in incidence descending order:

- Any TEAE
  - Any either trial drug related TEAEs
  - Any Crinone only related TEAEs
  - Any Duphaston only related TEAEs
  - Any TEAEs related to both drugs
- Any serious TEAEs
  - Any either trial drug related serious TEAEs
  - Any Crinone only related serious TEAEs
  - Any Duphaston only related serious TEAEs
  - Any serious TEAEs related to both drugs
- Any AE by worst severity
  - Any either trial drug related TEAEs by worst severity
  - Any Crinone only related TEAEs by worst severity
  - Any Duphaston only related TEAEs by worst severity
  - Any TEAEs related to both drugs by worst severity
- AEs leading to death (AEs with Grade 5 or outcome “fatal” if grade 5 not applicable)
  - Any either trial drug related TEAEs leading to death (AEs with Grade 5 or outcome “fatal” if grade 5 not applicable)
  - Any Crinone only related TEAEs leading to death (AEs with Grade 5 or outcome “fatal” if grade 5 not applicable)
  - Any Duphaston only related TEAEs leading to death (AEs with Grade 5 or outcome “fatal” if grade 5 not applicable)
  - Any TEAEs related to both drugs leading to death (AEs with Grade 5 or outcome “fatal” if grade 5 not applicable)

---

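### AE and SAE percentages pool women followed about 2 weeks after transfer with women followed about 9, and no common-window table is planned

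*Protocol*

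**What the plan says.** **Summary measure.** Protocol 9.4.4 plans that "Number and percentage of patients with AEs or SAEs will be presented according to System Organ Class and the preferred term" and that "Safety Analyses will be performed using the Safety population". SAP 15.1.1 repeats the approach: "adverse events will be displayed in terms of frequency tables: by primary system organ class (SOC) in alphabetical order". SAP 8.2 defines the Safety population: "Include all subjects who have received at least one dose of study intervention after randomization". SAP section 9 makes the whole analysis population the default denominator. Its exception covers analyses tied to particular visits, which the AE tables are not.

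**Time at risk.** Randomisation takes place on the day of ET (Protocol 6.3.1). Under Protocol Appendix 4 the β-hCG test follows about 14 days later and a negative result ends participation: "If the result of the pregnancy assessment is negative, procedures related to End of Study visit will be performed". Women with a continuing pregnancy stay on treatment to the ongoing pregnancy assessment at about Day 63 (Protocol 4.1). AE collection runs from Visit 2 (Day -5) to the End of Study Visit (Protocol 8.3.1). The SAP's treatment-emergent window (15.1) runs from the first post-randomisation dose to the last dose.

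**Pregnancy-dependent events.** Protocol Appendix 3 states: "In this clinical study, any spontaneous abortion, ectopic pregnancy, should be considered as an SAE". Protocol 9.4.1.2 counts bleeding after the pregnancy test as an AE.

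**What is already separated.** Early abortion is expressed per clinical pregnancy (SAP 14.2). Luteal phase bleeding is also shown by β-hCG result and vaginal bleeding by visit (SAP 15.2.3). SAEs are also listed (SAP 15.2.2). Neither document plans an AE table over a common window, an AE rate per unit of exposure, or AE tables by pregnancy outcome. SAP section 13 mentions exposure in its title but specifies only a compliance percentage.

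**The concern.** Comparing safety between the arms is a stated secondary objective. Time at risk is fixed by a post-randomisation outcome that the regimens may themselves change, so randomisation does not make the two arms' observation periods comparable. A crude percentage then mixes two things: how often AEs arise per unit of time on drug, and how many women stay on drug long enough to have one. If pregnancy rates differ, the tables could show a difference in tolerability where none exists, or conceal a real one. Protocol 9.4.3 says the pilot's primary result will inform formal trials, and its AE tables are likely to be read in the same light.

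**Working it through.** **Inputs from the documents.** "This study plans on including 334 participants from a single reproductive center over 25 months", and allocation is 1:1, so 334/2 = 167 women per arm. The test is 14 days after ET and the ongoing pregnancy assessment is at Day 63. Collection from Day -5 adds 5 days. The documents give no expected AE or SAE percentage, so there is no figure of the plan's own to reproduce.

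**Step 1: time at risk.**
- From ET: 14 vs 63 days, ratio 63/14 = 4.5.
- From Day -5: 19 vs 68 days, ratio 68/19 = 3.6.

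**Step 2: spurious AE difference when the drugs are equally tolerable.** All of the following are assumptions: the same constant AE hazard h per week in both arms; exposure of 2, 5 and 9 weeks for test-negative, early loss and ongoing; early loss in 12% of women in each arm; ongoing rates of 45% and 53%. The test-negative shares are then 43% and 35%.

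Arm percentage = sum over outcome groups of share × (1 − exp(−h × weeks)).

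At h = 3% per week the individual risks are 5.8%, 13.9% and 23.7%.
- 45% arm: 0.43 × 5.8 + 0.12 × 13.9 + 0.45 × 23.7 = 14.8%.
- 53% arm: 0.35 × 5.8 + 0.12 × 13.9 + 0.53 × 23.7 = 16.3% (16.25% unrounded).
- Difference: 0.08 × (exp(−0.06) − exp(−0.27)) = 0.08 × (0.942 − 0.763) = 1.4 points.

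| h per week | 45% arm | 53% arm | Spurious difference | SE at 167 per arm |
|---|---|---|---|---|
| 1% | 5.3% | 5.8% | 0.5 | 2.5 |
| 3% | 14.8% | 16.3% | 1.4 | 4.0 |
| 5% | 23.1% | 25.2% | 2.1 | 4.7 |

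The SE is √(2p(1−p)/167) at the average percentage p. At 3% per week, 1.4/4.0 is about a third of one SE. Over ET to the test, both arms show the same 5.8%.

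**Step 3: other assumed rates.** Take a 10% AE risk per 14 days and 10% early loss in each arm.
- Ongoing 35% vs 35%: 21.0% vs 21.0%, no distortion.
- Ongoing 35% vs 45%: 21.0% vs 23.8%, +2.8 points.
- Ongoing 30% vs 50%: 19.6% vs 25.2%, +5.6 points.

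With AE risks of 5 to 20% per 14 days and ongoing rates 5 to 20 points apart, the range is 0.8 to 8.7 points. At 35% vs 45%, and 10% risk per 14 days, an AE rate 14% lower in the arm with more pregnancies (rate ratio 0.86) would appear as no difference. If all AEs start by Day 14, the distortion is zero.

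**Step 4: SAEs.** Three separate assumed scenarios give three different answers.
- Loss in 15% of clinical pregnancies, clinical pregnancy 40% vs 50%: miscarriage SAEs are 0.15 × 40 = 6.0% vs 0.15 × 50 = 7.5% of women. The arm with more pregnancies looks worse.
- Loss in 12% of all women in both arms, as in Step 2: 12% vs 12%, no difference.
- β-hCG positive in 55% of both arms, with losses in 20% vs 10% of women: ongoing 35% vs 45%, miscarriage SAEs 20% vs 10%. The arm with more ongoing pregnancies looks better.

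**The case against.** The strongest reply is that a crude percentage per treated woman answers a legitimate question: her total AE risk under the regimen, including the longer treatment that success brings. The trial is an exploratory pilot without formal testing, SAP 15.1 relies on summary statistics for AEs, and the distortion is usually well inside sampling noise. That stands. It is why the crude tables should stay and why this is an improvement rather than the repair of an invalid analysis.

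A second reply is that much is already separated: early abortion per clinical pregnancy, both bleeding endpoints by period, preferred-term rows that show abortion and ectopic pregnancy individually, and SAE listings. This also stands, but only in part. It leaves the general AE and SAE percentages untouched. Ectopic pregnancy falls outside the early abortion endpoint, which covers intra-uterine loss only. Overall vaginal bleeding is still divided by all ET cycles.

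A third reply concerns the obvious remedy. Rates per woman-week assume a roughly constant hazard. Suppose 10% of women in each arm have an AE, all before Day 14. The crude tables correctly show no difference. With the Step 2 shares, mean exposure is 0.43 × 2 + 0.12 × 5 + 0.45 × 9 = 5.51 weeks vs 0.35 × 2 + 0.12 × 5 + 0.53 × 9 = 6.07 weeks. The rates become 10/5.51 = 1.81 vs 10/6.07 = 1.65 per 100 woman-weeks, a false 9% advantage for the arm with more pregnancies. This stands in full, so woman-week rates should not carry the comparison.

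A reader might also infer that the arm with more pregnancies is bound to look less safe. The documents do not support that. They give no expected pregnancy rate for each arm and no AE timing. The effect vanishes if pregnancy rates are equal or AEs come early, and for SAEs it can reverse.

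**Conclusion.** The point holds as a structural weakness of modest size. The AE and SAE tables use one denominator for women whose post-ET time at risk differs about 4.5-fold according to the efficacy outcome, and nothing planned gives a comparison over equal time. The crude percentages can mislead in either direction if two conditions hold: pregnancy rates differ between arms, and AEs continue to arise after Day 14. Under equal hazards of 1 to 5% per week and ongoing rates of 45% vs 53%, the distortion is about 0.5 to 2.1 points, below half a standard error at 167 per arm. Only wide pregnancy differences combined with frequent AEs take it to several points. All hazards, loss shares and arm rates here are assumptions. For SAEs no direction can be stated in advance.

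**What to change.** Keep the crude tables in SAP 15.1.1 and add:

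- **(a) Main between-arm comparison:** AE and SAE percentages from ET to the β-hCG test, in all treated women. Define the window by the test date or visit name. The test is Visit 4 in the current protocol, whereas SAP 11.3 places randomisation, which falls on ET day, at visit 4.
- **(b) Descriptive supplements:** post-test AEs among β-hCG-positive women, and exposure duration with events per woman-week by arm. State that the first conditions on a post-randomisation outcome and that the second assumes a roughly constant hazard.
- **(c) SAE split:** spontaneous abortion and ectopic pregnancy summarised apart from all other SAEs.

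The cost is SAP wording and a few extra tables from dates already collected, with no change to trial procedures. The limits are that (a) says nothing about events after the test, and that the supplements in (b), which do reach that period, are not clean randomised comparisons.
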